9.0 Confidentiality, Privacy and Data Management

9.1 Confidentiality

Refer to the Data Plan Review Form.

10.0 Data and Safety Monitoring Plan

10.1 Periodic evaluation of data

Our data and safety monitoring plan will be under the jurisdiction of the PI, [name]. For this study, the main source of adverse events will be medication related. A potential adverse event includes a breach of data confidentiality. According to the Penn State College of Medicine IRB's Standardized Operation Procedure "Reporting and Review of Unanticipated Problems Involving Risks to Participants or Others", all participants and research staff who have direct interaction with the participant or with the confidential data of the participant, will be instructed to report any unexpected discomforts or any potential breach of confidentiality of participant's data to the Principal Investigator responsible for the related components of data collection involved. Within 12 hours of any reported event, the PI will gather detailed information on the episode (See 19.2). If the event is considered to be an unexpected adverse event or a serious adverse event (SAE) it will be reported promptly to the IRB. The IRB will conduct its independent review and decide whether the episode represents an unexpected problem or an SAE. After a confirmed episode of an unexpected adverse event or SAE, the IRB will decide what, if any, corrective action is required. A summary of all events will also be reported to the IRB at the time of annual review.

10.2 Data that are reviewed

Data that will be reviewed include any reported side effects, adverse events (see below) or complications from the study.

Adverse event: Any untoward or unfavorable medical occurrence associated with the subject's participation in the research, whether or not considered related to the study intervention.

Serious adverse event: Any event temporally associated with the subject's participation in research that meets any of the following criteria:

- Results in death;
- Is life-threatening (places the subject at immediate risk of death from the event as it occurred);

- Requires inpatient hospitalization or prolongation of existing hospitalization;
- Results in a persistent or significant disability/incapacity;
- Results in a congenital anomaly/birth defect;
- Any other adverse event that, based upon appropriate medical judgment, may jeopardize the participant's health and may require medical or surgical intervention to prevent one of the other outcomes listed in this definition (examples of such events include allergic bronchospasm requiring intensive treatment in the emergency room or at home, blood dyscrasias or convulsions that do not result in inpatient hospitalization, or the development of drug dependency or drug abuse); or
- Results in a severely debilitating situation for the subject, such as psychological distress, financial hardship or damaging impact on social standing or employability.

Unexpected adverse event: A adverse event is considered "unexpected" if it is not listed in the general investigational plan or protocol; or is not listed at the specificity or severity that has been previously observed and/or specified.

10.3 Method of collection of safety information

Data will be collected during study procedures and through reports from staff and participants.

10.4 Frequency of data collection

The principal investigator , [name] will promptly review documented adverse events and abnormal test findings to determine 1) if the abnormal test finding should be classified as an adverse event; 2) if there is a reasonable possibility that the adverse event was caused by the study intervention(s); and 3) if the adverse event meets the criteria for a *serious adverse event*. The PI, [name], will consult the study physician [name] as needed.

10.5 Individuals reviewing the data

All participants and research staff who have direct interaction with the participant or with the confidential data of the participant, will be instructed to report any unexpected discomforts or any potential breach of confidentiality of participant's data to the reference physician and Principal Investigator responsible for the related components of data collection involved.

10.6 Frequency of review of cumulative data

Not applicable.

10.7 Statistical tests

Not applicable.

10.8 Suspension of research

The report of a serious adverse event.

11.0 Risks

Medication: Suvorexant is a new class of approved hypnotic drug that acts as an orexin 1 /2 receptor antagonist, suppressing wakefulness. It has been approved for the treatment of insomnia in adults at a dose of 10 or 20 mg – for complaints related to sleep onset and/or sleep maintenance. Adverse reactions which were reported to the FDA included central nervous system depression, amnesia, hallucinations, complex sleep – related behavior,

exacerbation of symptoms of depression, suicidal ideation and potential substance abuse, and impaired next day mental alertness. Common, but less serious, reactions included somnolence, headache, dizziness, abnormal dreams, diarrhea, cough, sleep paralysis, and cataplexy like symptoms (1).

Suvorexant should not be used concurrently with alcohol or a CNS depressant. Suvorexant should not be given to patients to patients who have a hypersensitivity to drugs of the same class. Suvorexant should not be given to patients with narcolepsy, to patients with major depression or impaired respiratory function. The drug should be used with caution in patients with a history of alcohol or drug abuse; but, complaints about insomnia are highly prevalent in this group of patients – and insomnia is strongly associated with risk of relapse following a period of abstinence. While the patients in the proposed study will have a history of current alcohol or drug dependence, they are all in residence in a treatment facility where they will be closely monitored. We will be employing a modified abuse liability protocol to assess the relative risk of developing some form of dependence on suvorexant. Importantly, neither tolerance nor withdrawal effects were observed with suvorexant in the premarketing studies. Suvorexant was not self-administered in non-human primate models.

As per the exclusion criteria, we will not be including pregnant or nursing female patients or patients with a current or history of major psychiatric disorder including depression, schizophrenia, or bipolar disorder; and, we will be excluding patients with current suicidal ideation and/or a past history of suicidal behavior.

Actigraphy: There is no known risk to wearing the wrist actigraphs. A minor skin rash may develop from the wristband, but this risk is very slight.

Questionnaires: The interviews and forms are routine, standardized forms for sleep research and psychology research. They pose no known risks, although certain questions may be mildly upsetting because they may probe sensitive psychological areas and others inquire about family history of medical and psychological illness or alcohol and substance use. Appropriate referrals are offered if areas of concern arise in the course of collecting this information. Research participants are free to skip any questions that make them uncomfortable.

Loss of confidentiality: The main risk of allowing us to obtain limited health information for research is a potential loss of privacy.

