3.2 Exclusion Criteria

- 1. Patients who are concurrently receiving a psychoactive drug for the treatment of an Axis I disorder, but not including sedating antidepressants trazadone or mirtazapine that have been prescribed for the treatment of sleep disturbance.
- 2. Patients with current major depressive disorder greater than mild or moderate, schizophrenia, bipolar disorder, or a history of traumatic brain injury.
- 3. Patients with a history of narcolepsy or REM related phenomenon.
- 4. Patients with chronic respiratory problems including asthma, COPD, or other respiratory issues that can lead to sleep disturbances at night.
- 5. Patients with current suicidal ideation or a history of previous suicide attempts.
- 6. Patients with severe liver impairment.
- 7. Women who are pregnant or breastfeeding.
- 8. Patients who are severely obese.
- 9. Decisional impairment
- 10. Prisoners or under legal mandate.
- 11. On any medication that would interfere with study participation

Page 5 of 27 (v.04/27/2020)

- 12. Hypersensitivity to medications in the same class as suvorexant
- 13. Any chronic conditions or exclusionary criteria that would prevent participation in the study or lead to participant at risk of untoward effect because of participation in the study.

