7.2 Study Procedures

When a medication is studied for a new indication, or in a new population, it is common (in clinical neuropsychopharmacology) to conduct the first study in an open trial. We plan to study two groups of patients in an open 7-day trial of 20 mg suvorexant HS, following a two-day baseline during which patients will be taking a previously prescribed sleep medication (i.e. trazodone, mirtazapine, or melatonin) before switching to suvorexant. The study design includes a combination of assessments, and the collection of biological samples. Participants will be enrolled in the study for a total of 10 days (9 nights). Table 1 references the daytime questionnaires and procedures, and Table 2 represents the night questionnaires and procedures. Night is considered to be the time after the patient takes the medication. In our study, the night falls after the day.

Table 1. Daytime questionnaires and procedures.

Study Day	0	1	2	3	4	5	6	7	8	9
Consent and										
Screening (Form										
90 AI/DI, MINI	X									
Screen/MINI 7.0.2,										
HAM-D)										
EMA		X	X	X	X	X	Χ	X	X	Χ
Modified ISI	Χ									Χ
Modified PSQI	Χ									
DNA Collection*	Χ									
Cortisol Collection		X	X					X	X	
Abuse Liability			X						X	
Battery – Morning			Δ						Λ	

Table 2. Night questionnaires and procedures.

Study Night	0	1	2	3	4	5	6	7	8
Suvorexant			1	2	3	4	5	6	7
Baseline**	X	X							
Suvorexant Administration			X	X	X	X	X	X	X
Actigraphy/Logs	Χ	X	X	X	X	X	X	X	X
Abuse Liability Battery - Night		X						X	
Observer Rated Questionnaire		X						X	

*Optional saliva for patients with opioid use disorder only

**Current medicine regime including antidepressants/melatonin

Abbreviations: EMA, ecological momentary assessment; ISI, Insomnia Severity Index; PSQI, Pittsburgh Sleep Quality Index.

7.2.1 Consent and Screening: Study Day 0

After signing the informed consent document, the Caron based study coordinator will complete a comprehensive screening assessment with each participant to further evaluate their eligibility in the study. The comprehensive screening assessment includes questionnaires to evaluate psychiatric comorbidities, sleep quality, depression and previous drug/alcohol use. The screening assessment questionnaires will be administered to the patients by the Caron based study coordinator on paper/ electronic tablet using the REDCap software. The screening questionnaires will include:

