• The M.I.N.I International Neuropsychiatric Interview (M.I.N.I. 7.0.2; if applicable) (10) which provides psychiatric diagnosis.

• The Hamilton Depression Rating Scale (HAM-D; 11) will be used to provide a continuous measure of depressive symptomatology and severity.

• The Form 90-AI or Form 90-DI (12) will be administered to assess recent and lifetime history of drug and alcohol use, respectively. Recent substance use will document the 90 days prior to residential treatment admittance.

- The Pittsburgh Sleep Quality Index (PSQI; modified) (13) will be used to document the subjective severity of sleep complaints.
- The Insomnia Severity Index (ISI; modified) (14) will measure insomnia related symptoms. This assessment will also be administered on Study Day 9.

The study coordinator at Caron will also provide the patient with an actigraph, sleep log and EMA smartphone which the patient will return after completing the study.

Optional Research: Participants who are being treated for opiate dependence will be asked if they would like to give a DNA sample from saliva using an Oragene collection kit to be used for DNA extraction. This is not mandatory. The samples will be stored at Department of Psychiatry, Penn State Hershey Medical center until the end of the study. When the study is complete, the samples will be shipped to [name] at University Park who will process the data for genotyping. He will purify the DNA from the saliva in his laboratory. Genotypes will be established from approximately 5 million sites in the genome. Candidates for single genes to study include the opioid receptor genes and the alcohol dehydrogenase genes. He will include these new genes in the analyses of the relation between suvorexant and opioid use. In addition to testing for genotype (the bases present in DNA), he will test for patterns of DNA methylation, which is an underpinning of epigenetics.

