Multiple domains of affect will be drawn from the Extended version of the Positive and Negative Affect Scale and assessed on a daily basis at the four established collection times (PANAS-X; 15). Items included will cover the circumplex spectrum, and include hostility, guilt, sadness, stress, anxiety, fatigue, and happiness. Similarly, formatted items will be used to assess the occurrence and degree of participants craving (16) within each of the 4 EMA surveys. In addition to items inquiring about mood, stress, and craving, the morning assessment will include subjective items related to sleep. These sleep items will record estimated time to fall asleep, night-time wakenings, quality of sleep, daytime sleepiness, and the nightly experience of dreams that involve alcohol/drug content. Two identical and brief mid-day surveys will inquire about mood, stress, and craving to capture aspects of late day experience such as 12 Step meeting attendance and patient perceptions about their day. Thus, our study will be able to capture both the variability in affect/craving and the temporal ordering of stressors and affect necessary to characterize within-day reactivity as well as changes observed in subjective and objective indices of sleep associated with suvorexant administration.

The smart phones that will be used for EMA data collection will have a security application installed that prevents user access to all other applications that are not associated with survey data collection. Smart phones will not be activated on a cellular network resulting in the disabling of voice, text, and internet functions. Research staff will use brief in-person meetings (every other day) as a means to ensure devices are being charged, build rapport, answer participant questions, monitor compliance, and to manually download data for backup storage on the RAs laptop and then uploaded to a secure server, Virtual COLO, at University Park in State College, PA. The server has all of the latest security updates applied as well as the physical security of the data center itself. The only people with access to the server are [name], [name], and [name]. Access to the web-facing application is controlled by CoSign (The standard university login system). Only encrypted communications are used to and from the device, and there is only access to the database through the localhost. The database containing user responses will be backed up periodically (hourly).

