Diurnal cortisol: (Study Days 1,2,7,8) Saliva will be collected for cortisol measurement at 5-time points for two consecutive days at two different periods in the study, i.e. 8:00 AM before breakfast, 12:00 PM before lunch, 3:00 PM, 6:00 PM and 9:00 PM. The research staff will visit with the participant at approximately 3 PM (Day 0, 6, 9), 8 AM and 3 PM (Days 1, 2, 7, 8) to

provide fresh cortisol collection kits needed for the next collection and to collect provided saliva samples. Instructions on how to provide saliva samples will be given to the participant on Day 0. Specimens are collected using a cotton swab kit (Salivette, item #51.1534). It has been demonstrated that five samples are adequate to examine circadian variation of cortisol secretion. Cortisol levels will be determined using a commercially-available, high-sensitivity salivary cortisol enzyme immunoassay kit (Catalog # 11-CORHU-E01-SLV; Alpco, Salem, New Hampshire) designed to standardize the measurement of salivary cortisol across research and biomedical laboratories. Saliva cortisol assaying will be done by a certified lab technician in the research laboratory at the Penn State College of Medicine.

7.2.3 Abuse liability: Study Nights 1, 7, and the days following it (Study Days 2 and 8)

Abuse liability will be assessed with a modified protocol which includes the abuse liability battery morning, abuse liability battery night and the observer rated questionnaire. It is based on questions used in previous studies of abuse liability (17). The abuse liability –night battery will be completed by each research participant 30 min after medication administration on study Nights 1 and 7. The abuse liability battery – morning will be completed the morning after drug administration on study Day 2 and 8. The abuse liability battery- morning and night has the same questions related to drug liking, drug value questionnaire, drug effects questionnaire except that there are additional questions asking to categorize the medication effect to one of the seven classed of psychoactive substances on the abuse liability battery-night . The observer rated assessment will be completed by the medication nurse as described below. Our primary measures of abuse liability on the abuse liability battery- morning, night and the observer rated assessment will include the following 5 measures:

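### Section 11 names worsening depression and suicidal ideation as suvorexant risks, but the HAM-D is given on Day 0 only, no listed on-treatment item asks about suicidal thoughts, and EMA mood has no described safety review

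*Combined protocol and SAP*

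**What the plan says.** Section 11 gives the reactions reported to the FDA, including "exacerbation of symptoms of depression, suicidal ideation and potential substance abuse, and impaired next day mental alertness", and separates them from a list of common, less serious ones. Section 3.2 item 5 excludes "Patients with current suicidal ideation or a history of previous suicide attempts". Item 2 of the same section excludes current major depressive disorder only when it is more severe than moderate.

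Section 7.2.1, headed "7.2.1 Consent and Screening: Study Day 0", includes the HAM-D among the screening questionnaires: "The Hamilton Depression Rating Scale (HAM-D; 11) will be used to provide a continuous measure of depressive symptomatology and severity". Table 1 marks the row holding the HAM-D and MINI at Day 0 and nowhere else. Of the screening scales, only the modified ISI is said to be repeated: "This assessment will also be administered on Study Day 9". Suvorexant is given on Study Nights 2 to 8 (section 7.2.4).

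Two scheduled sources of information run through the treatment period. EMA surveys are given four times a day on Days 1 to 9 (section 7.2.2), and of their affect items the protocol says: "Items included will cover the circumplex spectrum, and include hostility, guilt, sadness, stress, anxiety, fatigue, and happiness". Nurses also ask each patient about adverse events at every nightly administration, on all nine nights (section 19.2). In addition, an observer-rated form is completed 30 minutes after dosing on Nights 1 and 7 (sections 7.2.3 and 7.4.4).

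**The concern.** Section 11 puts three kinds of psychiatric risk in one sentence: worsening depression, suicidal ideation and substance abuse. Substance abuse gets its own battery, once at baseline (Night 1 and Day 2) and once on drug (Night 7 and Day 8). The other two get a baseline rating and no dedicated on-treatment instrument.

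Section 8.2 says the findings will be used to plan a future study. If the final report says that no suicidal ideation was seen, a reader will want to know whether patients were asked. As the protocol stands, that cannot be answered. For depression, EMA will show mood over time, but there will be no follow-up value on the scale used to describe patients at entry.

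The population makes this more than a formality. Section 2.3 describes dysphoria and emotional pain after withdrawal, and mild or moderate major depression is allowed in under section 3.2. Patients taking trazodone or mirtazapine, which section 7.4.1 describes as antidepressants, switch from them when suvorexant starts.

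**Working it through.** This is a check of the schedule. No power or sample size figure is involved.

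**Reproducing the plan's own count.** Section 7.2.2 gives four EMA surveys a day over nine days: 4 x 9 = 36, which matches its stated figure of about 36 per person.

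**Splitting it at the first dose.** The first suvorexant dose is on Night 2, and the protocol counts night as following day. Surveys on Days 1-2 therefore precede suvorexant: 2 x 4 = 8. Surveys on Days 3-9 follow it: 7 x 4 = 28. Check: 8 + 28 = 36.

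**Scheduled per patient after the first dose (section 19.2 questioning counted on all seven dosing nights):**

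| Measure | Source | Count | Asks about suicidal thoughts? |
|---|---|---|---|
| HAM-D or MINI | Table 1, 7.2.1 | 0 | not given |
| EMA mood surveys | 7.2.2 | 28 | no such item listed |
| Nightly adverse event questioning | 19.2 | 7 (Nights 2-8) | content not specified |
| Observer-rated form | 7.2.3, 7.4.4 | 1 (Night 7) | content not specified |

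If the nightly questions are asked at administration, the Night 2 enquiry comes before any suvorexant effect. That leaves 7 - 1 = 6 enquiries (Nights 3-8) after at least one earlier dose. None follows the Night 8 dose.

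**Who looks at the EMA mood data, and when?**
- Section 7.2.2: the phones are off any network. Staff meet the patient every other day, and the reasons given are charging, rapport, questions, compliance and backup. Missed surveys may be filled in afterwards on paper.
- Section 8.3: EMA mood appears as an outcome expected to improve.
- Section 10.2: the data reviewed for safety are side effects, adverse events and complications. EMA responses are not mentioned.
- Section 10.6: periodic review of cumulative data is marked not applicable.

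So worsening mood would be recorded, but no step is described by which someone would read it for safety during treatment.

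**Is there room for a repeat?** Section 7.2.2 says "The research staff will visit with the participant at approximately 3 PM (Day 0, 6, 9", and adds morning and afternoon visits on Days 7 and 8. Day 6 follows four suvorexant doses (Nights 2-5). Day 9 follows all seven and already carries the ISI. Section 16.5 already provides for coordinators to be trained on the HAM-D.

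**A related inconsistency.** Section 3.2 item 2 allows mild or moderate current major depressive disorder. Section 11 says, citing the exclusion criteria, that patients with current or past major psychiatric disorder, depression included, will not be enrolled. It also says the drug should not be given to patients with major depression. These statements cannot all describe the same enrolled population.

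**The case against.** The strongest reply is that the protocol is far from blind to these risks. Mood is surveyed 28 times after the first dose. Nurses actively ask about adverse events every night, so reporting is solicited. Staff make six cortisol-related visits after dosing starts (Day 6 once, Days 7 and 8 twice each, Day 9 once). The principal investigator, a licensed psychologist, is on call (section 16.4). Patients live in a facility where section 11 says they will be closely monitored, and section 19.2 requires immediate reporting of adverse events.

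All of this stands, and it rules out several stronger readings. A reader might infer that no scheduled measure can detect either risk, that patients must volunteer symptoms, or that mood goes unmeasured. EMA and the nightly questioning contradict each of these. A reader might also count zero assessments over 36 x 7 = 252 patient-nights. That holds only for the HAM-D, MINI and described suicidality instruments. It leaves out EMA and nightly questioning, and it assumes all 36 complete when section 8.1 expects 10 + 15 = 25 evaluable data sets.

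Nor does the HAM-D wording, "will be used to provide a continuous measure of depressive symptomatology and severity", promise repeated measurement. Set beside the MINI's diagnosis, it reads naturally as a graded score, so a single administration is no contradiction.

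Two further objections limit the remedy. A Day 9 HAM-D documents change after the last dose and cannot detect anything in time to act. In an uncontrolled study its change could not be attributed to suvorexant. Both are right. They bear on what the HAM-D repeat can show, and are the reason a nightly question is proposed as well.

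Finally, the nurse script, adverse reaction form, observer form and full EMA item set are not reproduced, and the EMA list is worded so that it need not be exhaustive. What those forms omit cannot be asserted.

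**Conclusion.** A narrow gap stands. Per patient, after the first dose, the protocol schedules no HAM-D or MINI and describes no item on suicidal thoughts. It schedules 28 mood surveys with no described safety review. Worsening mood is therefore measured but not monitored for safety. Detection of suicidal ideation rests mainly on nightly adverse event questioning that is not described as covering it, with other staff contacts as a backstop.

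This rests on the items the protocol lists. If an unreproduced form already asks about self-harm, the protocol need only cite it, and that part of the point falls away. The absence of a follow-up HAM-D, and the conflict between section 3.2 and section 11 over depression at entry, stand either way.

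The point does not touch the planned efficacy analyses. It affects what the pilot can say about two risks that it names itself, and the change should be made because it is cheap.

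**What to change.** 1. In section 19.2, add one direct question on worsening mood and thoughts of self-harm to the nightly nurse questioning. Positive answers would use the immediate reporting route to the site physician already stated there. Clinical handling stays with the site. This avoids having to read off-network EMA phones in real time.
2. In Table 1 and section 7.2.1, repeat the HAM-D at the Day 9 contact, and at the last contact for early leavers who are still in residence. In section 8.3, report the Day 0 to Day 9 change descriptively as a safety summary, and state that without a control group it cannot be attributed to the drug. The change in sleep medication at Night 2 is a further reason for that caution.
3. Reconcile section 3.2 item 2 with section 11 on whether patients with depression may enter. Which statement should govern is for the investigators.

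The cost is one more use of a scale for which coordinators are already to be trained, at an existing visit, and one added question a night: a few minutes of patient and staff time.
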